13.2 BASELINE ASSESSMENTS DURING SCREENING

Baseline assessments will occur over a 14-day period. If a subject fails to provide the required six urine specimens, including three positive for urine BE, and the accompanying other baseline repeated measures within the 14-day period, the baseline period may be shifted until the subject meets the requirements in any consecutive 14-day period but within 30 days before randomization. Potential participants will not be provided with the results of the urine analysis for BE. Screening assessments are considered valid if the subject is randomized onto the study within 30 days of the start of screening. However, the subject may not be randomized on the last day of the baseline assessment period. If the subject does not meet the requirements within the 30 days, then the informed consent process and all of the screening and baseline assessments must be repeated before subject randomization.

Baseline assessments include three-times weekly urine BE plus creatinine measurements, vital signs, urine drug screen, and self report of use (SUR), including cocaine, opiates, nicotine, alcohol, and marijuana for two weeks. BSCS, CGI-S, and CGI-O will be assessed once per week for two weeks. Subjects must have 6 vital signs and weight assessments performed in a consecutive two-week period. Assessments should be performed when urine specimens are collected. Ideally no more than 4 assessments should be obtained in one week of the two-week baseline.

13.3 SUBJECT RANDOMIZATION AND ENROLLMENT

If the individual meets all of the study inclusion and does not meet the exclusion criteria (a checklist will be provided in the CRF package – see form 1) then the subject can be randomized into the study. The investigator or study coordinator will call the CSPCC ITTRS and review the eligibility criteria and provide information such that adaptive randomization procedures can be followed including:

- Subject's gender
- Subject's ADD status
- Amount of cocaine used in the last 30 days
- HAM-D score

The ITTRS will provide the caller with a non-sequential subject number. The investigator or coordinator will arrange for investigational agent to be dispensed and arrange for the first visit of the subject to initiate treatment.

13.4 DOUBLE-BLIND TREATMENT

At the first clinic visit, subjects will be given instructions on how to apply patches and will be given a week's supply of patches (10 total). At study visits, investigative staff will remove old patches and apply new study patches. The site of the removed patch will be inspected for a reaction. Subjects will be scheduled for treatment and assessments three times per week usually on a Monday, Wednesday, and Friday, for 8 weeks. Two consecutive days may be scheduled around holidays or other schedule conflicts. All subjects will be provided an opportunity for HIV testing. All subjects will be provided with HIV/AIDS education (Appendix III). All subjects will

be provided with manual-guided psychosocial therapy once per week during the 8 weeks of treatment.

13.5 PREVENTION OF STUDY DROP-OUTS

Subjects will be encouraged to come for treatment and for the evaluation sessions as described in this protocol. To minimize missed sessions, they will be compensated for their transportation and time spent in completing study assessments. It will be emphasized to subjects during screening that even if they have a relapse they should come to all scheduled appointments. They will be discouraged from using cocaine, but there will be no penalty for relapsing, or for missed sessions.

13.6 PREMATURE STUDY TERMINATION

Since an intent-to-treat paradigm is being used for this study, subjects will be encouraged to continue completing study visits, study assessments and psychosocial treatment sessions, even if they are unable to tolerate investigational agents. If a subject decides to drop out of the study prior to week 8, s/he will be asked to complete all final assessments (termination) at the time of drop out (see section 14.3). If a subject wishes to stop taking drug but to continue to participate in psychosocial treatment, s/he will continue to have all scheduled assessments according to the protocol and will complete the study at week 8. During the period of psychosocial measures safety and efficacy data will be collected with the exception of data strictly related to patch use. Section 14.5 details the procedures to be followed in the event that a subject dies while participating in the study.

13.7 FOLLOW-UP

At the end of study week 8, subjects will asked to come to the clinic four weeks later for a final follow-up visit and assessments. If it is possible to have the subject return to the clinic, a urine specimen for BE will be collected and the subject will be asked to provide a current self-reported cocaine and other drug use, current treatment for drug or alcohol abuse, and an impression of the study medication. If it is not possible to arrange for the subject to return to the clinic, then they should be telephoned and asked to provide a current self-reported cocaine and other drug use, current treatment for drug or alcohol abuse, and an impression of the study medication. If a subject cannot be contacted directly, attempts will be made to reach the individual(s) previously identified by the subject as a contact source.

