TREATMENTS: A STS patch (STS: $1.0 \text{ mg/cm}^2 \times 20 \text{ cm}^2$ patch) or matching placebo patch will be worn for 24 hours and replaced daily for the 8-week duration of the study. All subjects will receive manual-guided psychosocial therapy weekly during the 8 weeks of treatment.

DURATION OF THE STUDY: The total duration of study participation for each subject will be a maximum of 16 weeks consisting of: screening to be completed within 30 days prior to randomization including a 14-day baseline assessment period; double-blind medication (8 weeks); and, follow-up evaluation conducted 4 weeks following completion or termination from the study.

SAFETY ASSESSMENTS: All candidates for study enrollment will have a physical examination, a 12-lead ECG and clinical laboratory studies (blood chemistry, hematology, and urinalysis) performed during screening. During the treatment phase, vital signs will be taken at each visit for the first two weeks and weekly thereafter. Assessments of adverse events (AEs), concomitant medications, and a urine screen for other substances of abuse will be performed weekly. An HIV Risk Assessment Battery will be used to characterize the population HIV risk behaviors (screening and week 8). At treatment week 8, or at the time of study discontinuation, subjects will be evaluated by AE assessment, vital signs, physical examination, clinical laboratory studies, and ECG.

EFFICACY ASSESSMENTS: Success in reduction of cocaine use will be determined by comparing the weekly mean proportion of cocaine non-use days (self-report confirmed or disproved by urine BE level at each study visit) in both treatment groups. Secondary assessments include overall proportion of cocaine non-use days, proportion of successful subjects, the largest number of consecutive cocaine non-use days, weekly mean quantitative urine BE levels, Addiction Severity Index (ASI) score, HAM-D score, Brief Substance Craving Scale (BSCS) score, Clinical Global Impression scores as assessed by the subject (CGI-S) and an observer (CGI-O). ASI is performed during screening and at the first visit of week 5 and at the end of week 8. The BSCS, CGI-S, and CGI-O are performed weekly during the 14-day baseline assessment period and the first visit of each study week. The HAM-D is performed during screening and every two weeks during treatment.

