14.1 ASSESSMENTS AT SCREENING/BASELINE

Prior to enrollment on the study, subjects will be screened to determine if they meet eligibility requirements. In addition, certain baseline assessments will be made that are part of eligibility determinations but also provide physiological, psychological, and disease status information prior to active treatment. Because the initial assessments are intensive, they have been separated into groups designated as screening and baseline assessments. The screening and baseline assessments should be conducted concurrently as scheduling permits.

14.1.1 Screening Assessments:

Screening assessments to be completed within 30 days of randomization (unless otherwise indicated) include:

- 1. Complete medical history and physical exam.
- 2. Psychiatric evaluation including assessment of adult ADD and SCID evaluation for DSM-IV diagnosis of cocaine dependence and Axis-I disorders.
- 3. ASI evaluation
- 4. HAM-D evaluation
- 5. Hematology
- 6. Blood chemistries
- 7. Routine urinalysis
- 8. Urine drug screen
- 9. Infectious disease panel
- 10. Rapid Plasma Reagin (RPR) test for syphilis
- 11. RAB
- 12. ECG
- 13. Pregnancy test (if female) within 2 days before study agent administration.
- 14. Blood sample as a control for assessments of selegiline/selegiline metabolite levels.

15. Prior medications. All medications taken by the subject for the 60 days prior to the first day that the subject receives study agents will be documented on a Prior Medication CRF. Data will be reviewed and recorded on the day that the subject first receives study agents but before study agent administration.

Assessment	Screening	Baseline										Termin-	Follow-
C4 1 XV. 1	(aamnlatad	within 30 days				1	1	1	1	1	1	ation ^a	up
Study Week		lomization)		1	2	3	4	5	6	7	8		12
Screening													
Informed Consent	Х												
SCID	Х												
Psychiatric	Х												
evaluation													
ADD	Х												
Medical History	Х												
Infectious disease	Х												
panel/RPR			-										
Safety			R										
Physical exam	Х		Α									Х	
Prior Medications	x ^b		N										
Vital Signs/weight		3 X/week for 2 weeks	D	3X	3X	Х	Х	Х	Х	Х	Х	Х	
Hematology	Х		Ο				Х					Х	
Blood Chemistry	Х		Μ				Х					Х	
Routine Urinalysis	Х		Ι				Х					Х	
12-lead ECG	Х		Ζ									Х	
Pregnancy test	(completed within 2 days before agent administration)		Α				X					Х	
Adverse Events			T	Х	Х	Х	Х	Х	Х	Х	Х	Х	Х
Con. Meds.			Ι	Х	Х	Х	Х	Х	Х	Х	Х	Х	
Efficacy			0										

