14.4 ASSESSMENTS AT FINAL FOLLOW-UP

Final off-treatment assessments will be performed four weeks after the 8 week period of doubleblind treatment and include:

- 1. Questions regarding amount of cocaine/other substance used over the last 4 weeks, current treatment for drug or alcohol abuse, and an impression of the study medication.
- 2. Urine BE and creatinine
- 3. AEs

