14.6.17 Adverse Events (AEs)

AEs will be assessed at each study visit by an investigative staff nurse or physician. If an AE is reported to a nurse that requires medical attention, it should be reported to a study physician immediately. A study physician will meet with the participant once a week to review the AEs recorded by the nurse and to assess for any additional AEs. The investigator or study physician will assess subjects for any medical or psychiatric side effects. Both the research assistant and physician will assess AEs by asking the participant "How have you been feeling since I saw you last". The type of AE, severity of the AE, and the relationship to the study treatments will be recorded on an AE CRF according to the procedures described in section 15.6.

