15.6 RECORDS RETENTION

Clinical records for all subjects studied, including history and physical findings, laboratory data, and results of consultations, are to be maintained by the investigator in a secure storage facility. These records are to be retained until notified in writing by the sponsor.

15.7 ADVERSE EVENTS REPORTING.

In accordance with FDA reporting requirements, all AEs occurring after randomization, and up to 4 weeks after completion of treatment, will be collected, documented, and reported by the investigator or sub-investigators according to the specific instructions detailed in this section of the protocol and Appendix V. The occurrence of AEs will be assessed weekly and an AE CRF completed.

An AE is defined as any reaction, side effect, or untoward event that occurs during the course of the clinical trial, whether or not the event is considered medication-related or clinically significant. For this study, AEs will include events reported by the subject, as well as clinically significant abnormal findings on physical examination or laboratory evaluation. A new illness, symptom, sign or clinically significant clinical laboratory abnormality or worsening of a pre-existing condition or abnormality is considered an AE. Stable chronic conditions, such as arthritis, which are present prior to clinical trial entry and do not worsen, are not considered AEs. All AEs must be recorded on the AE Form. The AE Form is also used to record follow-up information for unresolved events reported on previous visits.

Each week, a study investigator must review the AE Form completed for the previous week for any events that were reported as continuing. All AEs, including clinically significant abnormal findings on laboratory evaluations, regardless of severity, will be followed by study investigators until satisfactory resolution. AEs will be reported up to 4 weeks following completion of, or termination from, the study.

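### The off-treatment follow-up is timed from two different starting points, and its telephone fallback has no adverse-event question

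*Protocol*

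**What the plan says.** **Timing.** Two places count from when the subject leaves or completes. The synopsis, under duration of the study, describes a "follow-up evaluation conducted 4 weeks following completion or termination from the study". Section 15.7 closes its AE rule with "AEs will be reported up to 4 weeks following completion of, or termination from, the study". An earlier sentence in 15.7 gives a slightly different end-point: four weeks after treatment is completed, with no mention of termination.

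Three places count from the end of the planned treatment period. Section 13.7 has "At the end of study week 8, subjects will asked to come to the clinic four weeks later for a final follow-up visit and assessments". Section 14.4 has "Final off-treatment assessments will be performed four weeks after the 8 week period of doubleblind treatment". Table 1 puts the follow-up column at study week 12.

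**Content.** For the clinic visit, 13.7 names a urine specimen, self-reported drug use, current treatment and an impression of the medication. For subjects who cannot return, "then they should be telephoned and asked to provide a current self-reported cocaine and other drug use, current treatment for drug or alcohol abuse", again with an impression of the medication. AEs are in neither list. Section 14.4 does list AEs (item 3), Table 1 marks the "Adverse Events" row at follow-up, and 14.6.17 states that "AEs will be assessed at each study visit by an investigative staff nurse or physician". Section 14.4 describes no telephone route.

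**Subjects who leave.** Sections 13.6 and 13.12 ask them for the termination assessments of 14.3, which include AEs. Neither schedules a further contact four weeks later.

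**The concern.** Section 15.7 creates a duty to collect AEs for four weeks after a subject completes or leaves. A schedule should supply a contact at which that duty is met. For completers it does. For subjects who leave before week 8, only the synopsis supplies one; the sections that sites work from day to day (13.7, 14.4 and Table 1) put the contact at week 12 for everyone. For subjects who cannot return, the contact has a stated list of questions, and AEs are not on it.

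Safety is one of the trial's stated objectives. Two groups have weaker off-drug AE capture if 13.7 and 14.4 are followed as written: early leavers, through long recall, and subjects reached only by telephone, through the missing question. A subject in both groups is exposed to both weaknesses.

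**Working it through.** No power or alpha calculation is involved. The check sets the sections side by side and does simple timeline arithmetic.

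**Step 1: starting point.** Let w be the study week at the end of which a subject leaves.

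- AE window closes (15.7, second statement): w + 4.
- Follow-up contact on the synopsis timing: w + 4.
- Follow-up contact on the 13.7, 14.4 and Table 1 timing: 8 + 4 = week 12.
- Lateness of the week-12 contact relative to the window: 12 − (w + 4) = 8 − w weeks.
- Time from leaving to the week-12 contact: 12 − w weeks.

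| Leaves at end of week w | AE window closes (w + 4) | Contact under 14.4 | Lateness (8 − w) | Weeks since leaving (12 − w) |
|---|---|---|---|---|
| 8 (completer) | 12 | 12 | 0 | 4 |
| 6 | 10 | 12 | 2 | 6 |
| 4 | 8 | 12 | 4 | 8 |
| 2 | 6 | 12 | 6 | 10 |

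On the synopsis timing, lateness is zero in every row. On either timing the contact falls at or after the close of the window, so the window lies wholly inside the look-back period. What changes is the length of recall. The AE prompt in 14.6.17 is a single open question about how the subject has felt since last seen, so at w = 2 it would have to span 10 weeks.

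**Step 2: who is affected.** Subjects who stop the patch but stay in the study keep all scheduled assessments to week 8 (13.6), so the timing conflict does not touch them. It concerns those who leave. Section 16.6 quotes retention of about 70% in other studies. If that applied here, 300 × (1 − 0.70) = 90 subjects would leave early. The protocol gives no distribution of leaving times, so the values of w above are illustrative.

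**Step 3: content of the contact.**

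| Source | Clinic visit | Telephone contact |
|---|---|---|
| 13.7 | AEs not listed | AEs not listed |
| 14.4 | AEs listed | Route not described |
| Table 1 | AEs marked at follow-up | Route not described |
| 14.6.17 | AEs at each visit | A call is not clearly a visit |
| 15.7 | General duty to collect | General duty to collect |

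For the clinic visit, 13.7 is an incomplete list that three other places complete. For the telephone contact, nothing turns the general duty in 15.7 into a question that is asked. Section 14.6.17 also sends the reader to 15.6 for AE recording; 15.6 is records retention, and the AE rules are in 15.7.

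**The case against.** The strongest reply is that the protocol already secures AE collection. Section 15.7 places the duty on the investigator whatever the visit schedule says. It also requires AEs to be followed until they resolve, so events open at termination are not abandoned. Serious events must be telephoned in within 24 hours (15.8), and subjects who leave because of a serious event must have medical monitoring. Leavers are asked for termination assessments that include AEs. Section 13.7 can be read as the completers' schedule, with the synopsis governing those who terminate. On that reading there is no gap in timing.

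Much of this stands, and it rules out several stronger readings.

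- A reader might infer that the AE window is not covered at all for early leavers. It is covered late: the week-12 contact falls after the window closes and the question looks back.
- A reader might infer that the follow-up visit omits AEs. It does not; 14.4, Table 1 and 14.6.17 all include them.
- A reader might infer that telephone contacts yield no AE data. The missing item is not a prohibition, and 15.7 still applies.
- A reader might infer that intolerance or suicidality concentrates in early leavers. No section says so.

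What the reply does not remove is the conflict itself. Section 14.4 and Table 1 make no exception for early leavers, and 13.6 and 13.12 send them only to the termination assessments. A general duty also does not put a question on the telephone list.

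**Conclusion.** Two defects stand. First, the follow-up is timed from completion or termination in the synopsis and the second statement of 15.7, but from the end of the 8-week period in 13.7, 14.4 and Table 1. If 14.4 is followed, the scheduled AE contact for a subject leaving at week w comes 8 − w weeks after the 15.7 window closes, and the AE record for that period rests on delayed recall. Second, the telephone fallback has no AE question anywhere in the protocol, although 15.7 requires AEs for four weeks.

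The lateness figures follow directly from the stated weeks. The figure of about 90 early leavers assumes that the retention quoted from other studies applies here. How many subjects would be reached only by telephone cannot be estimated from the protocol. The point should be corrected, because following 13.7 and 14.4 as written gives poorer off-drug AE data in these two groups. It does not show that AEs would go uncollected.

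**What to change.** - Reconcile the starting point of the follow-up across the synopsis, 13.7, 14.4, Table 1 and both statements in 15.7, so that a scheduled AE contact matches the 15.7 window for subjects who leave early.
- Add an AE question to the telephone list in 13.7, including the status of AEs open at termination.
- For the clinic visit, have 13.7 refer to 14.4 rather than carry its own partial list.
- Correct the reference in 14.6.17 from 15.6 to 15.7.

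A question to the subject's named contact person about hospitalization or death would be an optional addition; its absence is not an error.

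The cost is wording in a few places and one question on an existing contact, with no extra visit. The one downside arises if the contact is timed from termination: early leavers' follow-up cocaine-use report would no longer fall at a common week 12.

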13.8 MAO-I SAFETY

No significant changes in blood pressure have been observed in the Somerset sponsored clinical trials in depression or in the NIDA clinical pharmacology studies with cocaine and STS. Based on studies performed by Somerset, tyramine dietary restrictions have been removed from STS protocols. In the unlikely event of a hypertensive crisis and/or STS overdose, the transdermal system should be discontinued and the underlying skin washed with soap and cold water to remove any residual investigational agent.

Vital signs will be measured to detect a pressor response in subjects receiving MAO inhibitors. Full reliance should not be placed on blood pressure readings, and the subject should also be observed for clinical signs of a sympathomimetic reaction. Accordingly, clinical judgment should be exercised regarding discontinuation of investigational agent if symptoms such as palpitations, tachycardia, sense of constriction in the throat or chest, or frequent headaches occur during the trial.

Subjects will be instructed to report promptly the occurrence of headache or other unusual symptoms, i.e., palpitations and/or tachycardia, a sense of constriction in the throat or chest, sweating, dizziness, neck stiffness, nausea, or vomiting.

Subjects will be cautioned not to take concomitant medications, whether prescription or OTC medications, without consulting the site investigator or physician designee.

13.9 MAINTAINING AND BREAKING STUDY BLIND

The decision to break the study blind for an individual subject lies with the site investigator and study principal investigator or with the NIDA medical monitor, but should be resorted to only in cases of life-threatening emergency when knowledge of the treatment arm investigational agent will influence clinical management.

13.10 PARTICIPANT REIMBURSEMENT

Subjects will be compensated for time involved, in providing data, and inconvenience, at a rate of \$10 per clinic visit during which a urine specimen is provided in the screening phase and \$10 per clinic visit during the treatment and follow-up phases upon completion of the specified requisite assessments. The maximum payment is \$370. Subjects will be compensated regardless of whether they continue to receive study medication. It is emphasized that this remuneration is for time and inconvenience (e.g., gasoline, public transportation, etc.), not for protocol compliance. Subject reimbursements may be made by cash or vouchers in accordance with local site policies. Subjects (or potential subjects as is the case during screening) should be paid on a daily or weekly basis, whichever is most convenient/acceptable locally.

